#### **4. Data Safety Monitoring Plan**

As this is a case series within standard of care procedures, steps to minimize risks to the confidentiality of identifiable information will be taken as with all HIPPA compliant services delivered at the Clinic. Data will all be labeled with the participants' assigned ID number. Protected Health Information will be kept separate from data and ID numbers in a Stanford University School of Medicine encrypted database to which only the PI and research assistants will have access. Psychological effects of study participation or breeches in confidentiality will be monitored and discussed at research meetings. There is a slight risk of motion sickness so participants will be closely monitored while immersed in the virtual scene, and if there is any discomfort they will be removed from the virtual environment. Participants are free to discontinue participation at any time. Any situation requiring medical attention will be promptly provided.

Given that participants enrolled are clinically depressed, suicidal ideation will be assessed each session. If it is revealed that a participant is expressing suicidal ideation, the clinician will conduct a thorough risk assessment in real time and a safety plan will be created. If it is determined the participant is an imminent danger to themselves, the clinician will initiate a 5150 hold and walk the participant to the hospital.

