## **1. Purpose of the Study and Background**

### **1.1 Purpose of the Study**

The primary aims of this study are to assess the feasibility, acceptability, and tolerability of a virtual reality (VR) behavioral activation (BA) treatment for individuals diagnosed with major depressive disorder (MDD). The secondary aim of this study is to explore the efficacy of using VR to deliver BA therapy to a clinical MDD population.

The primary hypothesis of this study is that VR is an acceptable, feasible, and safe way to deliver a BA intervention for individuals diagnosed with MDD. Acceptability will measure the participant's desire to continue using the VR treatment after the study ends, the participant's satisfaction with the VR treatment, the participant's use of the headset, and the participant's acceptance of VR treatment. Feasibility will look at how well VR can integrate into the BA therapy. Tolerability will measure simulator sickness and agitation while using the VR headset.

A secondary hypothesis is that VRBA will have stronger effects than BA treatment as usual or a waitlist control in treating individuals with MDD due to increased homework compliance. This is due to the research that has illustrated that homework compliance is one of the strongest predictors of treatment outcomes for BA. This hypothesis will be assessed by running t-tests comparing the change in PHQ-9 scores at timepoints across the three study arms.

This study will also comment on the following questions: Can one successfully deliver BA without the movement component, simulating just the experience of pleasure/ mastery? Does VRBA lead people to want to engage in real-life activities? Is the active ingredient of BA emotion or movement? Movement during the VRBA will be measured with the headset.

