In the first session, psychoeducation around the connection between behavior and mood will be discussed. Participants will then be introduced to BA. Participants will consider activities they enjoy as well as be provided with an activity list. Participants will be asked to select at least four activities that are highly enjoyable to schedule into their upcoming week. The VRBA participants will be required to choose VR activities for the week and the BA treatment as usual participants will be required to choose real-life activities to participate in. The VR participants will complete an activity in VR during session, in order to learn how to use the headset, which they will take home. Each time the participant finishes an activity in VR, he/she will be asked to complete a questionnaire assessing “spatial presence,” “simulator sickness,” “agitation measure,” and acceptability. Participants will also be asked to rate their mood on a scale of 1-10 (1=worst they ever felt; 10=best they ever felt) before and after their chosen activity. During session 2 and 3, clinicians will check in regarding goal attainment, work on barriers to completion of activities, assess depression scores, and introduce a new activity goal. During session 4, the treatment and skills will be reviewed, and feedback will be attained.

The participants randomized to the waitlist control group will be administered the PHQ-9 via phone on a weekly basis for four weeks. If item 9 is endorsed, a risk assessment will be conducted in real-time, and proper measures will be taken in accordance with risk. After the four weeks are completed, these participants will be given the option to simply remain on the clinic waitlist or choose to partake in 4 weeks of VRBA or BA treatment as usual. Only the data during their time as a waitlist control will be used in the study.

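### The protocol's only sickness-specific VR safeguard can work only in session, while most planned week 1 VR use is at home, and sickness ratings are tied to finished activities

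*Protocol*

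**What the plan says.** **Safeguard.** Section 4 of the protocol names motion sickness as a small risk. The control it gives is that "participants will be closely monitored while immersed in the virtual scene, and if there is any discomfort they will be removed" from the virtual environment. The sentence is not limited to sessions. The same section adds two general safeguards: participants may leave the study whenever they wish, and medical attention is promised where needed.

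**Planned use.** Section 3.1 of the protocol says of session 1: "The VR participants will complete an activity in VR during session, in order to learn how to use the headset, which they will take home". Participants are asked to "select at least four activities that are highly enjoyable to schedule into their upcoming week", and for this arm "The VRBA participants will be required to choose VR activities for the week". At sessions 2 and 3 the clinician is to "work on barriers to completion of activities, assess depression scores, and introduce a new activity goal". The size of that new goal, and whether any further VR takes place in session, are not stated.

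**Measurement.** Section 1.1 says: "Tolerability will measure simulator sickness and agitation while using the VR headset". The primary hypothesis is that "VR is an acceptable, feasible, and safe way to deliver a BA intervention". Section 3.1 sets the trigger for the ratings: "Each time the participant finishes an activity in VR, he/she will be asked to complete a questionnaire", which covers sickness and agitation among other things. Under Aim 1 Analysis, the SAP scores sickness (SSQ) out of 48 and agitation (BAM) out of 18 after rescaling. It averages each participant's scores and then gives intention-to-treat and completer averages. Dropout, adverse events and headset-use counts are tabulated under feasibility.

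**The concern.** There are two separate problems.

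**(a) The control does not match where the exposure happens.** Watching a participant and taking them out of the scene requires someone to be present. Section 3.1 places most of the first week's VR at home. Neither document describes a rule to stop at discomfort, remote monitoring, or a way to report between sessions for that use. The exclusion criteria in Section 2.6 screen for recent seizures and untreated epilepsy but not for susceptibility to motion sickness, so Section 4's sentence carries the load.

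**(b) The measure may leave out the worst uses.** Tolerability is defined over headset use, but the rating is requested on finishing. A removal rule produces unfinished activities by design, and a participant who feels ill at home may stop unprompted. If those uses go unrated, the loss is not random: they are the ones expected to score highest. The averages would then err towards the primary hypothesis.

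**Working it through.** **The plan's own scale.** The SAP's worked example has one symptom at 1, one at 2 and one at 1, out of 16 × 3 = 48. So 4/48 = 8.33% intolerability, which reproduces its figure. The plan states no home share and no rated share, so there is nothing else to reproduce.

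**(a) Home share of planned VR activities**

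Inputs from Section 3.1: in-session activities described = 1; scheduled for the coming week, h ≥ 4.

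- In-session activity additional to the four (the natural reading, since the four are for the week ahead): h/(h + 1) = 4/5 = 80% at least. With about 10 planned VRBA participants this is 40 of 50.
- In-session activity counted as one of the four: 3/4 = 75%.

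Later weeks need assumptions:

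| Assumption | Home share |
|---|---|
| Four per week for three weeks, no further in-session VR | 12/13 = 92% |
| Four per week for three weeks, one VR activity in each of 4 sessions | 12/16 = 75% |
| Four in week 1, one in each of weeks 2 and 3, VR in all 4 sessions | 6/10 = 60% |

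Home use is the majority in every row. These are planned counts, not completed activities, durations or sickness risk.

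**(b) Effect of unrated stopped uses**

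For participant *i*, let *m* be the mean score of rated uses, *s* the share of uses stopped and unrated, and *d* how much higher those uses would have scored. Then:

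- mean over all uses = (1 − s)m + s(m + d) = m + s·d
- reported mean = m, so the shortfall is s·d.

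If the group figure is a mean of participant means, the group shortfall is the average of the participants' own s·d values. A participant whose every use was stopped has no *m* and would be missing altogether. The documents give neither *s* nor *d*.

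Illustration with assumed scores: four finished uses at 4/48, and one stopped use (s = 1/5).

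| Score the stopped use would have had | Mean if unrated | Mean if rated | Shortfall |
|---|---|---|---|
| 12/48 | 8.3% | (16 + 12)/5/48 = 11.7% | 3.3 points |
| 24/48 | 8.3% | (16 + 24)/5/48 = 16.7% | 8.3 points |
| 36/48 | 8.3% | (16 + 36)/5/48 = 21.7% | 13.3 points |

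This shows how one missing rating acts on one participant's mean. It does not estimate what happened in the trial.

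**The case against.** **Other safeguards exist.** Freedom to discontinue, medical attention and the weekly barrier discussions all apply to home users, and the questionnaire itself records sickness. This stands, so a reader should not infer that home users had no protection. But none of these says how sickness at home is noticed between sessions or acted on. The removed consent pages may hold a home-use instruction; if so, what remains is that Section 4's sentence needs its scope stated.

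**The 80% is conditional.** This also stands. A reader might take it as a floor for the whole course. It is one only if the learning activity is extra to the four and no other VR is done in session. The conclusion needs only a majority in week 1, which holds on both readings.

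**The rating gap rests on one word.** If finishing was meant to include stopping early, there is no gap. A reader might infer that the tolerability results are biased. The documents do not support that, because nothing shows that any use was stopped or that a stopped use went unrated.

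**Warning signs are already tabulated.** Dropout, adverse events and use counts would reveal some trouble. They do not enter the SSQ and BAM averages, and no rated-use count is set beside them.

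**Waitlist calls.** A reader might extend the point to these, since Section 4's step of accompanying someone to hospital cannot be done by phone. Section 3.1 gives those calls their own rule: a real-time risk assessment, with measures matched to the risk. The extension therefore fails.

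**Conclusion.** The point holds in two limited parts.

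- **Safeguard.** Section 4's sickness-specific control cannot be carried out in the setting where most planned week 1 VR use takes place: 4/5, or 3/4 on the less favourable count. This rests on the planned numbers in Section 3.1 and on no home procedure being given in the available text.
- **Measurement.** Taken literally, the trigger for the ratings can omit uses stopped for discomfort, which would make VR look more tolerable. The direction is clear and the size unknown. It is zero if no use was stopped or if stopped uses were rated.

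The weight is minor to moderate. Tolerability is a primary aim and safety is part of the primary hypothesis, but the SAP sets no tolerability threshold, so no formal decision would change. What is affected is how far the descriptive averages can be trusted, in a study whose SAP reports fewer participants than planned.

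**What to change.** 1. **Protocol, Section 4.** Limit the monitoring and removal statement to in-session use. Add a home rule: stop at any discomfort, report it, and have the clinician follow up before the next use.
2. **Protocol, Section 3.1.** Request the questionnaire after every started VR use, finished or stopped, with the reason for stopping.
3. **SAP, tolerability tables.** For each participant, show the number of headset uses, the number rated and, where recorded, the number stopped for discomfort. Count uses and ratings in the same unit, because one wearing of the headset could cover several activities.

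The SAP is written in the past tense. If data collection is complete, only item 3 applies, and items 1 and 2 are for further enrolment or a follow-on study.

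**Cost.** Item 3 needs two or three columns: use counts are already planned, and rated uses can be counted from the questionnaires. Items 1 and 2 need a few sentences and one added question per use. The downsides are slightly more burden after an unpleasant use, some stopped uses still going unrated, and stopped counts that may not be recoverable from existing records. This is a cheap improvement.

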#### **5. Preliminary unpublished data:** There is no preliminary data to date.

# **Virtual Reality Behavioral Activation: An Intervention for Major Depressive Disorder**

**NCT04268316**

**April 13, 2021**

**Aim 1:** To evaluate whether using VR to administer a brief BA protocol is a feasible, acceptable, and tolerable treatment for individuals diagnosed with MDD.

**Aim 1 Analysis:** The feasibility, or degree to which VR could successfully be integrated into the brief BA protocol, was measured by commenting on qualitative barriers to use observed. Barriers were assessed by rates of dropout, adverse events, the number of times the headset was used, and the level of presence experienced in the headset, all of which were represented in a table, as recommended by Birkhead et al. (2019). Level of presence was obtained by participant report from a Likert scale of 0 (not at all) through 4 (very strongly) for each question; and with three questions, there was a possibility of yielding a score between 0 and 12. The average total presence for each participant, intend-to-treat (ITT) participants, and protocol completers were then calculated and placed into a table. The average presence experienced was also calculated as a percentage by dividing the average score by 12 (the maximum score). Acceptability of the VR BA treatment was measured by participant report using the TAM, with the agreeance choice on the Likert scale represented from 0 (strongly disagree) through 4 (strongly agree). The number of questions in each category determined the outcome range (either 0-12 for three questions or 0-16 for four questions). Each participant's scores were then averaged and placed into a table, along with the average ITT participants and protocol completers' scores. The average percentage of acceptance was also calculated by dividing the average score by the maximum score in the outcome range. In order to determine the degree of

acceptance, as labeled on the scale, the average score was then scaled back depending on the number of questions. For example, the “Perceived Usefulness” category included three questions, yielding a potential range of 0 to 12, so an average score of 10 would be divided by 3 to assess the degree of acceptance (in this case it would yield a score of 3.33, which would correlate to “agree” on the Likert scale). Physical tolerability of the VR headset was assessed by participant report using the SSQ, and the emotional tolerability of the VR headset was assessed by participant report using the BAM, again represented in tables. Physical tolerability was broken into each item and ranged from 0 (no more than usual) through 3 (severely more than usual) for each item. Each participant’s scores were averaged and placed into a table, along with the average ITT participants and protocol completers’ scores. The total percentage tolerability rating for a given activity was calculated by dividing a participant’s score by 48, since there were 16 items, yielding a potential range of 0 to 48. For example, if a participant endorsed *nausea* slightly more than usual (1), *sweating* moderately more than usual (2), and *headache* slightly more than usual (1) during the VR activity labeled “Puppies,” then his/her percentage score would be calculated by dividing 4 by 48, to yield 8.33% intolerability or 91.67% tolerability during that activity. The percentage of intolerability for each symptom category was similarly calculated by dividing the average score by the maximum potential score of 3. The average scores for physical tolerability were summed for each participant and placed into a table, along with the average emotional tolerability scores of each participant. Emotional tolerability was scored from 1 (strongly disagree) to 7 (strongly agree) per question; and with three questions, there was a possibility of yielding a score between 3 and 21. These scores were rescaled to a range of 0 to 18 by subtracting 3 from all scores. The percentage of physical intolerability and

emotional intolerability were calculated by dividing the average scores by the highest potential score (48 for physical tolerability and 18 for emotional tolerability).

**Aim 2:** To assess whether VR BA is efficacious in treating the symptoms of MDD compared to BA as usual or a waitlist control.

**Aim 2 Analysis:** In order to determine any initial clinical efficacy of the VR BA treatment compared to BA treatment as usual and a waitlist control, participants' depression scores were measured using the PHQ-9 at four time points. With the goal of randomizing 30 participants, the average change between PHQ-9 scores at time 4 and time 1 for each of the three groups were going to be compared to one another. Example: Average change in PHQ-9 scores of group A (VRBA) was going to be compared to the average change in PHQ-9 scores of group B (BA treatment as usual). The average change in PHQ-9 scores of group A was going to be compared to the average change in PHQ-9 scores of group C (waitlist control). The average change in PHQ-9 scores of group B was going to be compared to the average change in PHQ-9 scores of group C. This change was going to be determined using independent samples t-tests.

However, given the lower-than-expected sample size, in order to assess initial clinical efficacy of the VR BA treatment compared to the BA treatment as usual and control groups, each group's mean as well as each participant's PHQ-9 scores were graphically represented across time. Additionally, each group's mean PHQ-9 change scores from time one through time four were graphically represented.

**Exploratory Aim 1:** To evaluate whether engaging in an activity in VR increases mood more than engaging in an activity in real life.

**Exploratory Aim 1 Analysis:** In order to evaluate whether engaging in an activity in VR increased mood more than engaging in an activity in real life, the differences in mood before

and after each VR activity were cumulatively added across each participant and then divided by the number of activities completed, in order to find the mean. The same was done for the BA treatment as usual group. For example, a participant who completed three total activities and reported a pre-activity score of 5 and a post-activity score of 6 for activity one, a pre-activity score of 3 and a post-activity score of 5 for activity two, and a pre-activity score of 8 and a post-activity score of 7 for activity three, would have a difference of 1, 2, and -1 respectively. These numbers would be summed to a total difference of 2, and then divided by the number of activities (3), to yield an average score change of .67 pre- to post-activity. These averages were represented in a table. Additionally, the reported pre- to post-activity mood changes of participants in the VR BA and BA treatment as usual group were tallied and graphically represented.

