## **3. Methods and Procedures**

### **3.1 Procedure**

Participants will be recruited from the clinic waitlist or through the study flyer. A total of 30 participants will be recruited, about 10 participants per study arm. These participants will be given the contact information of the protocol director. Upon reaching out to the protocol director, an informational phone script will be read to determine study eligibility and subject interest.

If subjects are interested and present with symptoms of depression, they will be invited to Stanford School of Medicine, Department of Psychiatry & Behavioral Sciences for an intake session. This session will include obtaining informed consent, the Mini International Neuropsychiatric Interview, and completing the demographic questionnaire. If subjects meet study eligibility, they will be randomized into either the VRBA, BA treatment as usual, or waitlist control arm of the study using 5 opaque, concealed envelopes in sets of 6 to preserve balance throughout the study. Participants will have a 1 in 3 chance of being randomized into each group. Participants will then be scheduled for their first treatment appointment.

The VR intervention will follow the protocol for Behavioral Activation (BA). Participants in the BA treatment as usual or VRBA arms of the study will meet with their clinician once per week for 50 minutes to receive BA therapy. These participants will complete the PHQ-9 at the

beginning of each session. If item 9 is endorsed, a risk assessment will be completed in real-time and appropriate actions will be taken.

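### The SAP answers the primary hypothesis with point rates and averages from about 10 VRBA participants and no statement of uncertainty, so a favourable table could be over-read as showing safety or feasibility

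*SAP*

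**What the plan says.** Protocol section 1.1 puts the primary question as a hypothesis: "VR is an acceptable, feasible, and safe way to deliver a BA intervention for individuals diagnosed with MDD". The SAP's Aim 1 replaces the word safe with tolerable.

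The Aim 1 Analysis handles each domain as follows.

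- **Feasibility:** commentary on barriers, supported by a table. "Barriers were assessed by rates of dropout, adverse events, the number of times the headset was used", together with the presence score.
- **Acceptability:** TAM category scores averaged for each participant, for ITT participants and for completers, shown as a percentage of the maximum and read back against the Likert labels.
- **Tolerability:** SSQ and BAM scores averaged and divided by their maxima (48 and 18).
- **Safety:** no analysis of its own. Adverse events appear only in the list of feasibility barriers.

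On size, Protocol section 3.1 says: "A total of 30 participants will be recruited, about 10 participants per study arm". The SAP's Aim 2 Analysis replaces its planned t-tests with graphs, "given the lower-than-expected sample size", without giving the number enrolled overall or by arm. Neither document gives a confidence interval, target rate or cut-off for any Aim 1 measure.

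**The concern.** Description is a sensible analysis for a small feasibility study. The difficulty is that it is paired with a hypothesis containing the words safe and feasible. A table showing no adverse events, little dropout and high percentage scores would look like confirmation. Without a measure of uncertainty beside the figures, nothing tells the reader how weak that confirmation is.

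The SAP acknowledges the small sample for Aim 2, where it withdraws the t-tests. It makes no matching allowance for Aim 1, although that is the primary aim and concerns one arm only. At stake is whether a later trial or clinical service takes a statement about safety or feasibility from this study that about 10 people, or fewer, cannot support.

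**Working it through.** **Inputs**

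- Planned total 30, about 10 per arm (Protocol 2.1 and 3.1).
- Allocation: "Participants will have a 1 in 3 chance of being randomized into each group" (Protocol 3.1).
- Achieved VRBA arm size: not given. I use 10 as planned and 5 as an assumed smaller arm, with intermediate sizes for range.
- Event rates for planning: none. Protocol section 5 reports no preliminary data. The true rates used below are assumptions for illustration.

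**Reproducing the plan's own figures**

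- Arm size: 30 × 1/3 = 10. If the envelopes are read as 5 sets of 6, then 5 × 6 = 30, which agrees.
- SSQ example: 4/48 = 8.33%, and 100% − 8.33% = 91.67%. Correct.
- TAM example: 10/3 = 3.33. Correct.
- No precision or power calculation is given, so there is none to reproduce.

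**Zero adverse events.** The exact (Clopper-Pearson) two-sided 95% upper limit for 0 of n is 1 − 0.025^(1/n).

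| VRBA arm | Upper limit for 0 events |
|---|---|
| 10 (planned) | 1 − 0.025^(1/10) = 30.8% |
| 8 (assumed) | 36.9% |
| 6 (assumed) | 45.9% |
| 5 (assumed) | 1 − 0.025^(1/5) = 52.2% |

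The probability of seeing no affected participant when the true proportion is p is (1 − p)^n.

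| Assumed p | n = 10 | n = 5 |
|---|---|---|
| 10% | 34.9% | 59.0% |
| 20% | 0.8^10 = 10.7% | 0.8^5 = 32.8% |
| 30% | 2.8% | 16.8% |

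**Dropout.** With x of n dropping out, the exact limits are the 0.025 quantile of Beta(x, n − x + 1) and the 0.975 quantile of Beta(x + 1, n − x).

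- 1 of 10: 0.3% to 44.5%
- 2 of 10: 2.5% to 55.6%
- 1 of 5 (assumed arm): 0.5% to 71.6%

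**Mean scores (presence, TAM, SSQ, BAM).** With the participant as unit, the half-width is t(0.975, n − 1) × SD/√n.

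- n = 10: 2.262/3.162 = 0.72 SD
- n = 5: 2.776/2.236 = 1.24 SD

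**The unfavourable direction.** If 8 of 10 dropped out, the exact interval would be 44.4% to 97.5%. That would be clear evidence against feasibility, so the weakness lies in what a favourable result can establish.

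**The case against.** The strongest case on the other side has four parts.

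1. **The study is descriptive and exploratory in size.** With no preliminary data, intervals and decision rules may seem out of place. This stands against demanding a test or a pass mark. It does not stand against showing the imprecision of a rate.

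2. **The plan already has anchors.** TAM means are read against Likert labels, so a mean in the disagree range would be hard to present as acceptance. Presence, TAM and SSQ means and average BAM scores are tabulated by participant, SSQ is also shown by item, and simulator sickness and agitation are asked about after every VR activity. This largely stands. A reader might infer that almost any result could pass as success, or that the primary question cannot be answered in either direction. The documents do not support either reading, as the anchors and the 8-in-10 calculation show. Participant tables show spread, but they do not show how far an observed dropout or adverse event rate may lie from the true one.

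3. **No conclusion has been drawn.** A reader might infer that the sponsor has declared the hypothesis supported. Neither document does so; they describe measures and tables. The concern is about how the tables may later be read.

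4. **A success mark is too late and would suit the size poorly.** The SAP is written in the past tense and already knows of the shortfall, so a mark set now would be post hoc. A rule based on the unfavourable limit would also fail a perfect 0 in 10 against any adverse event mark below 30.8%. This stands, and the fix therefore contains no such rule.

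**Conclusion.** The concern holds as a limit on favourable conclusions. With the planned arm of 10, no observed adverse event is compatible with a true proportion of up to 30.8%, one dropout is compatible with 0.3% to 44.5%, and a mean score is known to within about 0.72 SD. The SAP reports none of this uncertainty, so a favourable table could be taken to show safety or feasibility when common harm or frequent dropout has not been excluded.

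The figures rest on an arm of 10. If the VRBA arm shared in the shortfall, the imprecision is greater; the figures for 5 rest on an assumed arm size. Participants who chose VRBA after the waitlist period cannot enlarge the sample, because Protocol section 3.1 restricts the use of their data to the waitlist weeks. The 10%, 20% and 30% rates are illustrations.

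The data remain usable. This is an inexpensive improvement to reporting and wording, and it does not call for a larger sample or a formal test.

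**What to change.** In the SAP's Aim 1 Analysis:

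- State the number randomised to VRBA. Report dropout and the proportion of participants with at least one adverse event with exact (Clopper-Pearson) 95% intervals, using all randomised VRBA participants as the denominator.
- Report mean presence, TAM, SSQ and BAM scores with 95% intervals, using one averaged value per participant, since activities within a person are not independent. Give the number contributing to each mean, because someone who never completed a VR activity has no score. A t interval is only approximate for bounded scores in so few people, so keep the participant-level tables beside it.
- Add no success mark now, since neither document records one set before the data were seen.
- Word the Aim 1 conclusions as estimates with their uncertainty, and do not state that the hypothesis of safety, feasibility or acceptability is supported.

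The cost is a few table columns and some SAP wording, with no new data. The downside is that the conclusions will be more cautious.

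### The SAP's percentage of emotional intolerability reads 50% for a neutral participant and up to 33.3% for one who disagrees throughout, and it is not comparable with the SSQ percentage of the same name

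*SAP*

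**What the plan says.** Protocol section 1.1 states: "The primary aims of this study are to assess the feasibility, acceptability, and tolerability of a virtual reality (VR) behavioral activation (BA) treatment". The same section ties tolerability to simulator sickness and agitation in the headset, so the agitation measure is one of two components of that aim.

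The SAP's Aim 1 Analysis handles three instruments as follows.

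- **BAM (emotional tolerability).** "Emotional tolerability was scored from 1 (strongly disagree) to 7 (strongly agree) per question". There are three questions, so raw totals run from 3 to 21. "These scores were rescaled to a range of 0 to 18 by subtracting 3 from all scores". The percentage rule is then "emotional intolerability were calculated by dividing the average scores by the highest potential score (48 for physical tolerability and 18 for emotional tolerability".
- **SSQ (physical tolerability).** There are 16 items, each from 0 (nothing beyond the usual) to 3 (severe), with the total divided by 48. The result is also called intolerability.
- **TAM (acceptability).** Items are scored "with the agreeance choice on the Likert scale represented from 0 (strongly disagree) through 4 (strongly agree". A category holds three or four items, so its maximum is 12 or 16. "The average percentage of acceptance was also calculated by dividing the average score by the maximum score in the outcome range". The SAP then divides the average by the number of questions and reads the result as a scale label. In its example, an average of 10 on three questions is divided by 3: "in this case it would yield a score of 3.33, which would correlate to “agree” on the Likert scale".

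No such reading back to a label is described for the BAM. Neither the BAM nor the TAM percentage is given a neutral point or a threshold.

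**The concern.** The BAM and TAM run from disagreement to agreement, so their zero is the strongest possible disagreement and their middle is a neutral answer. Dividing by the maximum treats the score as an amount that grows from nothing. A reader who meets a figure of 33% emotional intolerability will take it as a moderate degree of distress. It can equally come from someone whose every answer lay on the disagree side.

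The SSQ is different. Its zero means no added symptom, and any positive percentage reports at least one. Using one word for both percentages invites the reader to set physical against emotional intolerability, and the scales do not allow that. What is at stake is the descriptive conclusion on a primary aim: VR could appear emotionally worse tolerated than it was. For the TAM the distortion would run the other way and make VR look better accepted.

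**Working it through.** **Inputs**, all from the SAP's Aim 1 Analysis: BAM, three items scored 1 to 7, 3 subtracted, divisor 18; TAM, three or four items scored 0 to 4, divisor 12 or 16; SSQ, 16 items scored 0 to 3, divisor 48.

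**Reproducing the SAP's own figures.** SSQ example: 4/48 = 8.33%, leaving 91.67%. TAM example: 10/3 = 3.33. BAM range: 3 × 1 − 3 = 0 to 3 × 7 − 3 = 18. All agree with the SAP.

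**BAM, same answer *a* on all three items:** percentage = (3*a* − 3)/18.

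| Answer | Rescaled score | Percentage of intolerability |
|---|---|---|
| 1 (strongly disagree) | 0 | 0% |
| 2 | 3 | 16.7% |
| 3 | 6 | 33.3% |
| 4 (midpoint) | 9 | 50% |
| 5 | 12 | 66.7% |
| 6 | 15 | 83.3% |
| 7 (strongly agree) | 18 | 100% |

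Answers confined to 1, 2 and 3 therefore give 0% to 33.3%.

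**TAM, same answer *a* on all *k* items:** percentage = *ka*/(4*k*) = *a*/4, whether *k* is 3 or 4. Answers of 0, 1, 2, 3 and 4 give 0%, 25%, 50%, 75% and 100%. Answers confined to 0 and 1 give 0% to 25%; neutral gives 50%.

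**Comparison with the SSQ.** If every SSQ item is one step above usual, the score is 16/48 = 33.3%. That equals the BAM figure for answers of 3 throughout. The first participant reports sixteen increased symptoms; the second, on the assumed scale, has agreed with no statement of agitation. The same percentage has two meanings.

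**Recovering the item mean.** Item mean = rescaled score/3 + 1. A rescaled score of 6 gives 6/3 + 1 = 3, on the disagree side. A score of 9 gives 9/3 + 1 = 4, the midpoint.

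**The case against.** The defence has several sound points.

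- **The rescaling is linear and disclosed.** Anchors, ranges and divisors are all stated, so a reader can recover the item mean. Subtracting 3 also removes the floor, so complete denial scores 0%. This stands. The fault lies in what the percentage is called and how it will be read, not in the arithmetic.
- **The TAM is largely covered.** The label read-back would place an average of 1 on the disagree side next to its 25%. This stands. A reader might infer that anyone rejecting VR scores 25% accepting, but 25% is the ceiling for uniform disagreement, and strong rejection scores 0%.
- **The percentages are not said to share a table.** A reader might infer that the two intolerability percentages are tabulated side by side. The SAP says that average physical and emotional scores share a table; the percentages are only said to be calculated. It also states no physical-versus-emotional comparison. What remains is the shared name, with both percentages defined in one sentence.
- **A large ratio between the scales would be an artefact.** One severe SSQ symptom gives 3/48 = 6.25%, and it is tempting to set this against 33.3% and call the gap fivefold (33.3/6.25 = 5.3). That compares all three BAM items with one of sixteen SSQ items. With one BAM item at 3 and the others at 1, the score is 2/18 = 11.1%, a ratio of 1.8. Neither ratio measures the fault.
- **Little hangs on the figure formally.** No test, threshold or decision rule uses these percentages, average scores are reported as well, and the BAM distortion works against the intervention. This limits the severity. But Aim 1 is reported only through such descriptive summaries, so no later analysis would correct a misreading.

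**Conclusion.** The point holds for the BAM. As defined, the percentage of emotional intolerability can reach 33.3% for a participant who disagrees throughout and equals 50% for a neutral one, so it does not express how intolerable VR was. It cannot be compared with the SSQ percentage of the same name. For the TAM the weakness exists (up to 25%, and 50% for neutral) but is mostly offset by the label read-back.

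This rests on three assumptions. The SAP labels only the ends of the BAM scale, so the meaning of answers 2 to 6, including 4 as neutral, is taken from their position on a symmetric scale. The item wording is not given; that agreement means more agitation follows from the SAP calling the score intolerability. For the TAM, that 1 means disagree is inferred by symmetry from the SAP reading 3.33 as agree.

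A reader might go further and conclude that the primary results as a whole are wrong. The documents do not support that: the SSQ percentage is unaffected, and the average scores are reported. This is a fault of labelling and interpretation on a primary aim, worth correcting before conclusions on tolerability are drawn.

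**What to change.** In the SAP's Aim 1 Analysis:

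1. For the BAM, replace the percentage of intolerability with the item mean on the 1 to 7 scale (rescaled score/3 + 1). Read it against the end anchors and the midpoint of 4, as the SAP already does in kind for the TAM. Give the item wording and any labels for the intermediate answers.
2. State that percentages of maximum from the BAM and the SSQ are not comparable. The SSQ percentage can stay.
3. For the TAM, lead with the label read-back and give the percentage second, if at all.
4. A count of participants whose BAM item mean lies above the midpoint is optional. The SAP is written in the past tense, so any such cut-off should be marked post hoc.

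The item mean has its own limit. A group mean of 3 can come from everyone answering 3, or from one third answering 7 and two thirds answering 1 (7/3 + 2/3 = 3). The per-participant averages that the SAP already tabulates should therefore stay beside it.

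The cost is wording and recalculation of collected data, and a summary slightly less simple than a single percentage. No new data are needed.
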